2. It is anticipated that AET will result in increased efficiency of neural processing during cognitive tasks in post measures compared to SC and with less difference than compared to HC compared to pre- intervention comparisons. Cognitive efficiency will be measured by the amplitude and latency of two event related electrical potentials associated with attention and conflict monitoring processing.
3. It is anticipated that concussed participants receiving the AET will exhibit improved balance. This will be measured using the force platform centre of pressure area, displacement, and velocity measures while completing the various static stance positions using the BESS protocol.
4. It is anticipated that concussed participants receiving the AET will exhibit increased improvements in salivary BDNF levels, indicative of an improvement in concussion symptoms. Salivary BDNF will be quantified using the BDNF ELISA assay and changes in pre- vs. post-intervention concentrations will be assessed. Additionally, we hypothesize that lower levels of BDNF upon entry to the study will indicate more pronounced concussive symptoms. This relationship will be determined by correlating the pre-intervention BDNF concentration to measures of the post intervention assessments.

5. It is anticipated that concussed participants receiving the AET will exhibit improved reaction times compared to the SC group during dual tasking scenarios to avoid crashing in dangerous traffic situations.

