The Flanker task is commonly used to test the ability to attend to central relevant information (the direction of an arrow) while disregarding irrelevant distracting stimuli (pairs of flanking arrows presented on either side of the central arrow). To identify the direction of the central arrow, participants will press a left or right button to indicate the direction of the central arrow. Data will be separated into time frames containing the components of interest (the N200 and P300). The session is concluded after completion of the oddball and flanker tests twice.

Behaviour Measure (Driving Simulator):

The performance of participants in a driving simulator will be assessed by measuring his/her reaction time and counting the number of passes and failures when anticipating potentially dangerous traffic situations. Reaction time will also be measured during dual-tasking activities. At a mutually agreed upon date and time, the participant will meet a member of the research team at the Sanders building, Lakehead University. A member of the research team will then escort he/she to the Centre for Research on Safe Driving (Braun Building, room 1024). Before beginning the assessment, the member of the research team will verbally restate the participant's rights and confirm that he/she is still willing to participate in the study. Participants will then be fitted with a POLAR SP0810 heart rate monitor before being introduced to the STISIM Drive[®] Model 400 driving simulator. Participants will be seated approximately 70% of his/her arm's length from the steering wheel with a backrest inclination of 10° (Majid et al., 2013; Yoo, An, Lee, & Choi, 2013)^{36,37}. The simulator will be connected to a PowerLab (16/30) data acquisition unit which will be interfaced with LabChart 7 software. Heart rate (HR), heart rate variability (HRV), and reaction time (RT) will be measured using LabChart 7.

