Participants will perform a 10 minute orientation drive to familiarized his/herself with the control and feel of the driving simulator. During the orientation drive, he/she will be exposed to examples of the dual tasking activities so that he/she will know how to successfully respond to the prompts. Once a participant feels comfortable with the simulator, the 20 minute simulation and data collection will begin. The simulation will be based on the Thunder Bay road system with traffic and pedestrians present. Weather will be clear and visibility will not be reduced. Reaction times will be measured during predetermined scenarios and will be recorded from the moment stimulus occurs to the moment the brake is depressed or evasive maneuver performed. Heart rate and HRV will be recorded throughout the duration of the simulation and will be marked at the beginning and end of each dual task scenario and reaction time activity. Participants will be exposed to several scenarios. These scenarios include: Vehicle incursion at intersection, pedestrian incursion from side of the road, sudden braking by a vehicle in front of participant, pedestrian incursion in school zone, braking by a vehicle in front of participant, and animal incursion (attached)

During dual task events, red triangles will be displayed over either of the side mirrors. These triangles will be deactivated by the press of a button on either side of the steering column, accounting for the dual tasking component of the reaction time scenarios. These scenarios will

have a three second threshold for time to react before the scenario will be considered a fail (National Safety Council, 2012; Triggs & Harris, 1982)^{38,39}.

In the event a participant is unsuccessful during a dual tasking scenario and collides with on screen stimuli, he/she will continue with the simulation with no second chance at completing that specific activity. If a participant begins to experience symptoms of simulator sickness, the scenario will be paused to allow him or her to take a break from the screen and/or have something to drink or eat. The research team member will have water on hand, if required by the participant. When he/she feels ready to proceed, the simulation will be resumed from the point of the original pause. If a participant feels that he/she is unable to continue, the simulation will be stopped and data collection terminated.

Aerobic and Balance Retraining Program:

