going through regular standard of care and healthy control on measures of reaction time for dual and non dual tasking driving events. The analysis will be performed pre and post intervention to examine the interaction effect between group and time on measures of reaction time. The statistical analysis will include descriptive statistics to calculate means and standard deviation for each group for the pre and post test data. A mixed factorial analysis of variance will also be performed with group as the independent factor, time (pre and post intervention) as the repeated measure and reaction times as the dependent variable to examine the effect of the AET.

Preprocessing and analysis may either occur on [name] recording computer using asa-lab software or a separate analysis computer (also password protected) using EEGLab software. Prior to analysis data will be segmented into epochs around each event (trial) presentation. Data will be temporally filtered. Baseline line correction using the 200 ms before the stimulus presentation will be applied. Artifact detection and removal will be applied to remove trials that have been affected by excessive head motion (for example blinking, general body movement). Once preprocess, all the trials from the same condition type will be averaged to create an event-related potential for each condition type. This data, for each participant will be exported for statistical analysis (performed in JASP). Repeated measures ANOVA will be used to determine if there are significant between group and between condition differences.

Missing data will be handled according to the type of data that is missing. For analyses that depend on change (pre- vs post-), if a participant misses an assessment (i.e saliva) we will have to exclude the participant's results for that assessment. If the rest of the assessments were completed pre and post intervention, then they will be included in the data analysis.

There will be no interim analysis.

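### Driving failures are counted but never analysed, and sections 10 and 11.2 do not say how a failed event enters the reaction-time ANOVA

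*Combined protocol and SAP*

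**What the plan says.** Section 7.2 (driving simulator) names two performance measures: reaction time, and "counting the number of passes and failures when anticipating potentially dangerous traffic situations". Reaction time is "recorded from the moment stimulus occurs to the moment the brake is depressed or evasive maneuver performed", with no upper cut-off in that definition. After describing the dual-task prompts, the section says the scenarios "have a three second threshold for time to react before the scenario will be considered a fail". A participant who is unsuccessful in a dual-task scenario and collides is not given a repeat: "he/she will continue with the simulation with no second chance at completing that specific activity".

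Hypothesis 5 (section 2) expects the AET group to "exhibit improved reaction times compared to the SC group during dual tasking scenarios".

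Section 10 compares the groups on "measures of reaction time for dual and non dual tasking driving events", using a mixed factorial ANOVA with "reaction times as the dependent variable to examine the effect of the AET". Section 11.2 lists ERP, balance, BDNF and reaction time as the dependent variables. Neither section gives a model for passes and failures. The missing-data rule in section 10 deals with a missed assessment, not with a failed event inside a completed drive.

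**The concern.** Two things are missing: an analysis of an outcome that is collected, and a rule for how failed events enter the outcome that is analysed.

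The second gap matters because failure is related to the quantity being measured. Reaction time ends at a brake press or evasive manoeuvre, so an event with neither has no value and leaves the ANOVA. If the analyst also leaves out every other failed event, each participant's mean is taken over successes only. An intervention that turns failures into slow passes then adds slow values to the post-intervention mean, which counts against the arm that improved. The share of events removed would differ by arm and visit whenever the intervention works or does harm, so randomisation does not protect the comparison. With no rule written down, the choice could also be made after the data are seen.

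**Working it through.** **Inputs.** From section 7.2: a 3 s limit and six scenario types listed. From section 5.2: 20 participants per group. The documents give no reaction-time mean, SD or failure rate, so there is no planned figure to reproduce. The medians and spreads below are assumptions.

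**Formulas.** Let T be log-normal with median m and log-SD s, let c = 3, and let z = (ln c − ln m)/s.
- Failure rate: 1 − Φ(z).
- Mean with all times kept: M = m·exp(s²/2).
- Mean with failures dropped: M·Φ(z − s)/Φ(z).
- Mean with failures set to 3 s: M·Φ(z − s) + 3·(1 − Φ(z)).

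**One case in full (s = 0.4).**
- Pre, m = 2.4: z = 0.558, failures 29%, full mean 2.600 s, passes-only mean 2.056 s.
- Post, m = 1.9: z = 1.142, failures 13%, full mean 2.058 s, passes-only mean 1.817 s.
- True gain: 2.600 − 2.058 = 0.54 s. Passes-only gain: 2.056 − 1.817 = 0.24 s, or 44% of the true gain.
- With failures set to 3 s and averaged, the gain is 0.36 s, so capping alone does not remove the shrinkage.

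**Other cases (s = 0.4).**

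| Median pre → post (s) | Failures pre → post | True gain (s) | Passes-only gain (s) | Lost |
|---|---|---|---|---|
| 2.4 → 1.9 | 29% → 13% | 0.54 | 0.24 | 56% |
| 2.0 → 1.7 | 16% → 8% | 0.325 | 0.18 | 44% |
| 1.2 → 1.0 | 1% → 0.3% | 0.22 | 0.20 | 8% |

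**Second set of assumptions.** Responses are 10% faster after intervention with the same coefficient of variation (CV, 0.3 or 0.5), and the baseline median runs from 1.2 to 2.4 s. Dropping failures keeps between 99% and 34% of the true change. For example, with median 1.8 s and CV 0.5, failures go from 14.0% to 9.6% and a true change of 0.201 s appears as 0.107 s (53% kept). Setting failures to 3 s keeps 76% in that example. If late times are measured and kept, nothing is lost.

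**The direction is not fixed.** With median 2.1 s at both visits and CV rising from 0.3 to 0.5, failures rise from 11% to 23%. The true mean worsens by 0.155 s, but passes-only shows an improvement of 0.177 s.

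**Effect on the group contrast.** This was simulated for AET against SC: 20 per arm, six events per visit, 15% faster in AET only, within-person CV 0.4, between-person log-SD 0.2, t test on change, 2,000 runs.
- Baseline median 2.1 s: all times kept, 0.355 s and 55% power; failures dropped, 0.181 s and 37%; failures set to 3 s, 0.249 s and 60%.
- Baseline median 1.5 s: 0.248 s and 53%; 0.193 s and 50%; 0.222 s and 54%.

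**Check on a participant median as remedy.** A median with failures recorded as 3 s is unaffected only while fewer than half of that participant's events fail. With six independent events and a 29% failure rate, the chance of three or more failures is 23%. In the first case above, the gain in the average participant median is then 0.46 s instead of 0.51 s: a small loss, but not zero.

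**The case against.** A reader might infer that every event passing three seconds has no usable reaction time, that the slowest responses are therefore removed, and that improvement is certainly understated. The documents do not support this.

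- No section says that failed events are dropped. The recording rule has no cut-off, so a brake press after 3 s can still be timed. A participant may also brake in time and still collide, which leaves a valid value. Only an event with no response necessarily lacks one.
- Understatement needs three things together: failures excluded (or capped), failures becoming fewer, and a similar spread. The example with rising spread shows the opposite sign.
- The three-second sentence follows the dual-task description, and the sentence on collisions names a dual-task scenario. The limit may therefore not apply to the non-dual events that section 10 also analyses.
- The six scenario types are introduced as examples, with a reference to an attachment. It cannot be said that one failure costs a sixth of a participant's data.
- The large losses come from assumed baseline medians close to the limit. Nothing in the documents favours a high failure rate over a low one. Driving is also one of five hypotheses.

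All of this stands, and it limits the claim. It does not supply the missing rule or an analysis of the failure count. On the narrow reading, the limit still falls on the dual-task events that Hypothesis 5 concerns.

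**Conclusion.** The plan collects a pass/fail outcome that it does not analyse, and it leaves open how failed events enter the driving ANOVA. Events with no response drop out under the plan's own definition of reaction time. Whether other failed events do is unstated.

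If all failures are excluded, the comparison is conditioned on success, and a uniform speed-up with similar spread is understated. The loss is negligible when failures are rare and about half when roughly 15–30% of events fail at baseline. If the spread changes, the bias can reverse. These sizes rest on assumed log-normal times and assumed medians. The failure rate that would settle the matter is not in the documents.

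The point affects one hypothesis and is of uncertain size, but it is cheap to put right and should be settled before the data are analysed.

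**What to change.** In sections 10 and 11.2:

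1. Keep every measured time to brake or evasive manoeuvre, including times beyond 3 s.
2. Treat events with no response as right-censored in an event-level mixed model of reaction time, with group, visit and their interaction. A simpler alternative is each participant's median over all events with fails ranked slowest, which is nearly but not fully unbiased when there are few events.
3. State that means will not be taken over passed events only.
4. Add a group-by-time mixed logistic model of the pass/fail outcome already collected.
5. In section 7.2, say whether the three-second limit applies to dual-task scenarios only or to all driving events.

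The cost is SAP wording and slightly more analysis. No new data or visits are needed. The downside is a summary less simple than a plain mean.

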3. EXPECTED RISKS/ BENEFITS

3.1 Expected Risks

Low intensity aerobic and balance exercise poses minimal risk for healthy individuals. Like all types of exercise, there is a slight risk of sustaining a musculoskeletal injury such as a sprain or strain. There is a small risk, however, when performing aerobic and balance exercises while experiencing PCS; participants may see an increase or worsening of his/her symptoms. In order to minimize this risk, exercise will begin at a very low intensity and gradually increase. All exercise sessions will be monitored by a research team member to ensure that the session is being completed at the proper intensity. Should a participant report any PCS during a session, the session will be stopped immediately. Furthermore, to ensure that participants are healthy enough to participate in exercise, all participants will be medically cleared by [name] prior to participating in the study.

There is a minor risk that, when using the driving simulator, participants may experience symptoms such as nausea or dizziness. Breaks will be allowed during the assessment in an effort to prevent this. Water will also be readily available during the assessment should the participant require it. If a participant experiences any of these symptoms and is unable to continue, the session will end.

Physical and cognitive assessment, neuroimaging, and biomarker assessment should pose minimal risk to participants.

There is a minor social risk with respect to confidentiality. This risk will be minimized by ‘de-identifying’ the personal information with codes. All names will be removed from data/samples. All data will be stored in an encrypted file on the secure Sync.com account on a password-protected computer in a locked office at LU. Any hard copies of data such as screening checklists or the IPAQ will be coded and stored in a locked filing cabinet in a secure office at LU ([name] current office, SB 1007). All saliva samples will be coded and stored in [name] secure lab.

The results of this study will be published with aggregate data, that is, data which is combined and summarized so that no individual participant can be identified.

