4.6 Participant Withdrawal Criteria

Withdrawal will occur upon participant request. A participant who wishes to withdraw consent from the study will be asked to specify if he/she wish for any data or samples collected to be withdrawn from the study. Samples and data will be withdrawn in accordance with the participant's wishes.

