After completing baseline assessments, PCS participants assigned to the AET intervention will complete an eight week supervised AET program. The program will consist of three sessions per week, approximately 40-60 minutes each. Each session will be completed under the supervision of a trainer with the Canadian Society for Exercise Physiology (CSEP-CPT) certification. At mutually agreed upon dates and times, participants will meet a member of the research team at the Sanders building, room SB-1025. Before beginning the intervention, the member of the research team will verbally restate the participant's rights and confirm that he/she is still willing to participate in the study. Participants will then be outfitted with a Polar F2 heart rate monitor, in order monitor exercise intensity during the session. Exercise intensity for each session will be based on the participant's heart rate reserve (HRR). At the first session, the participants HRR will be calculated using the Karvonen formula; Target Exercise Heart Rate = $((220 - \text{Age} - \text{Resting Heart Rate}) \times \% \text{Intensity}) + \text{Resting Heart Rate}$. Once the participant's HRR has been calculated, the participant will begin the aerobic component of the session.

The aerobic component of the session will be performed on a cycle ergometer. Participants will begin with a five minute warmup at a self selected speed, which will be used to bring the participant's heart rate to the desired intensity. Intensity for each session will start at 20% of HRR, and increase linearly by 10% for the first four weeks; at week four, participants will be cycling at an intensity of 50%. Weeks five and six will be performed at 55% of HRR, week seven will be performed at 60% of HRR, and week eight will be performed at 65% of HRR. Duration will follow a similar pattern for weeks one to four, beginning at 20 minutes and increasing in five minutes/week increments. At week five, duration will be reduced to 25 minutes, and then increase to 30 minutes for weeks six to eight.

Following completion of the aerobic portion of the session, participants will rest for five minutes before beginning the balance component of the session. Participants will perform three balance exercises (in order) each session: narrow based double leg stance, single leg stance, and tandem stance. Difficulty of these exercises will be progressively increased by modifying the

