12.4 Premature discontinuation or termination of the study

The study sponsor/investigator and the Research Ethics Board reserve the right to terminate this research study at any time. Reasons for termination include but are not limited to:

The occurrence of adverse events poses a potential health risk for participants;

Unsatisfactory participant enrollment;

Investigator request to withdraw from study;

Noncompliance with the protocol or regulatory guidelines are not being followed;

REB decision to terminate or suspend approval for the investigation or Investigator.

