14.7 Data Monitoring Committee

There will be no data monitoring committee.

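### The plan does not say what follows an AET session stopped for symptoms, and it ties the AET post-assessment to completing all 24 sessions

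*Combined protocol and SAP*

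**What the plan says.** Section 3.1 names the hazard of exercising with PCS: "participants may see an increase or worsening of his/her symptoms". Against it the section sets a low starting intensity with gradual increase, supervision ("All exercise sessions will be monitored by a research team member to ensure that the session is being completed at the proper intensity"), medical clearance "prior to participating in the study", and one rule that acts during exercise: "Should a participant report any PCS during a session, the session will be stopped immediately".

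Section 7.2 (Aerobic and Balance Retraining Program) fixes the cycling load by week of the programme: "Intensity for each session will start at 20% of HRR, and increase linearly by 10% for the first four weeks". Set percentages of HRR follow for weeks five to eight. Cycling duration and balance difficulty also go by week number. The same section places the AET post-assessment after 24 completed sessions.

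Section 4.6 gives one route out: "Withdrawal will occur upon participant request". Section 14.8 has all adverse events recorded and reported under the ethics board's guidelines. Section 12.4 allows the whole study to be ended, and one listed reason reads: "The occurrence of adverse events poses a potential health risk for participants". Under section 10, a participant who misses an assessment is excluded from the change analysis for that assessment.

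**The concern.** Section 3.1 treats symptoms during exercise as serious enough to end the session, but its instruction stops there. The next instruction a trainer has is the week's target in section 7.2, which for most weeks is higher than the last. A participant whose sessions are stopped repeatedly is therefore scheduled for the next step, and nothing available asks a clinician to look at the case. The schedule in section 7.1 shows no medical or symptom assessment between the pre- and post-intervention visits.

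That leaves the decision with the participant. Section 6.5 lets PCS participants keep the activity monitor if they complete the intervention, which gives some reason not to ask to stop.

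There is also a risk of bias. If exercise ends early for people who worsen, and the post-assessment is understood to follow 24 completed sessions, they may not be assessed. Section 10 would then remove them from the change analyses. The loss would fall on the AET arm and on those who did badly in it, so AET would look better than it was.

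**Working it through.** **1. The plan's own figure.** Section 7.2 states 50% of HRR at week four. Starting at 20% with three weekly steps of 10 points: 20 + 3 × 10 = 50. The figure is reproduced.

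**2. The full schedule (section 7.2).**

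| Programme week | 1 | 2 | 3 | 4 | 5 | 6 | 7 | 8 |
|---|---|---|---|---|---|---|---|---|
| Intensity, % HRR | 20 | 30 | 40 | 50 | 55 | 55 | 60 | 65 |
| Cycling, minutes | 20 | 25 | 30 | 35 | 25 | 30 | 30 | 30 |
| Intensity × minutes | 400 | 750 | 1,200 | 1,750 | 1,375 | 1,650 | 1,800 | 1,950 |

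Of the seven week-to-week changes in intensity, six are rises, one is flat (week 5 to 6) and none is a fall. The product of intensity and minutes eases once, at week 5, because duration is cut by 10 minutes. That easing is also fixed by week number.

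**3. What this means in heart rate.** The formula in section 7.2 is target = (220 − age − resting rate) × intensity + resting rate. The documents give no resting rates, so 60 to 80 bpm is assumed here.
- Age 50, resting 60: 110 × 0.20 + 60 = 82 bpm in week 1; 110 × 0.65 + 60 = 131.5, or about 132 bpm, in week 8.
- Age 18, resting 80: 122 × 0.20 + 80 = about 104 bpm in week 1; 122 × 0.65 + 80 = about 159 bpm in week 8.

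Across ages 18 to 50 and that range of resting rates, the target goes from 82–104 bpm to 132–159 bpm.

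**4. Search for an individual-level step after a stopped session.**
- 3.1: ends the session; silent on the next one. Clearance is before participation, with no repeat stated.
- 7.2: targets by week; no condition on symptoms, tolerance or stopped sessions. The check before the intervention confirms willingness to take part, not symptom status.
- 4.6: participant request, and nothing else listed.
- 12.1: concomitant care is allowed; this is not a review.
- 12.4: acts on the whole study, at discretion.
- 14.8: recording and reporting; no stated action for the individual.

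None supplies the step. By contrast, section 7.2 does set out pausing, resuming and ending for sickness in the driving simulator.

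**5. A related mismatch.** Section 4.4 requires at least one PCS symptom at entry, while the stop rule in 3.1 is set off by any PCS. Read literally, a symptom already present at entry could stop a session.

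**6. The bias.** If k of the 20 AET participants are not assessed, the mean change among those assessed differs from the mean for all 20 by (k/20) × (mean of those assessed − mean of those lost). Each person lost contributes 1/20 = 5% of that gap. The documents give no basis for k or for the gap.

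**The case against.** The best reply is that this is silence, not conflict. A reader might infer that 3.1, 4.6 and 7.2 contradict each other, or that 7.2 orders escalation whatever the symptoms. The text does not support that. Section 7.2 gives planned targets and never says they override a stopped session; section 4.6 deals with withdrawal of consent, data and samples; all three can be followed together. That participant request is the only route is itself inferred from nothing else being listed. Nor is worsening the trigger: 3.1 stops a session for any reported PCS, which is more cautious.

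The safeguards are also real. A certified trainer supervises every session, adverse events go to the ethics board under guidelines not available here, and participants may withdraw at any time (12.5). The consent materials were removed from the text supplied and may say more.

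On assessment, section 5.1 has all participants reassessed after eight weeks. One therefore cannot conclude that people who stop early will be missed, only that 7.2 leaves room for it.

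These points limit the claim. They do not supply the missing step: no available section connects a stopped session to what happens next for that person.

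**Conclusion.** The point holds as a gap with a safety and a bias consequence, and it should be corrected. Following the plan as written, a participant with repeated stops moves to the next weekly target, at six of seven steps a higher one, without a stated review. The post-assessment wording in 7.2, taken with section 10, could remove such people from the AET results.

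The size cannot be put in numbers beyond the schedule itself and the 5% of the arm that each lost participant represents, because the frequency of stops is unknown. The 20 × 24 = 480 planned AET sessions are a tempting measure, but that is every planned session, not the number affected. The lack of a data monitoring committee (14.7) should not be counted as evidence either: it says nothing about rules for individuals.

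The conclusion assumes that neither the consent materials nor the ethics board's reporting guidelines contain the missing step.

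**What to change.** 1. Reconcile 3.1, 4.6 and 7.2 so that they state how a session stopped for symptoms bears on the following sessions and on continued participation, and who reviews the case. Reconcile 3.1 with 4.4 on symptoms present at entry. The clinical content is for the investigators to set.

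2. Keep that review away from the team members blinded under 12.3. Exercise stops occur only in AET, so discussing them at the monthly team meetings, which the budget notes (16.6) also use for data analysis, could reveal allocation.

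3. Amend 7.2 so that the AET post-assessment is due at eight weeks rather than on completion of 24 sessions, in line with 5.1. State that AET participants whose exercise is paused or ended still attend it and are analysed in their assigned group.

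The cost is protocol wording, ethics notification and a little clinician time. That time is not in the budget: the 32 physician hours are already used, as 80 screenings × 0.25 h = 20 h plus 12 meetings × 1 h = 12 h. Some AET participants may also receive less than the full programme.
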